Therefore, in order to investigate the impact of face coverings on exercise capacity, research will take place in two phases:

Phase I: Participants will be randomized and complete 2 treadmill trials including (1) cardiopulmonary exercise tests (CPET) with face covering, and (2) CPET without face covering.

Phase II: Participants will be randomized and will complete 2 cycle ergometer trials including (1) cardiopulmonary exercise tests (CPET) with face covering, and (2) CPET without face covering. Cognitive testing will occur incrementally as exertion increases.

SPECIFIC AIMS & OUTCOMES

Phase I:

The proposed study consists of 4 specific aims:

Specific Aim 1: Describe the primary and secondary outcomes of athletes during a Cardiopulmonary Exercise Test (CPET) on a treadmill with (arm 1) and without (arm 2) the use of a face covering.

Specific Aim 2: Conduct a randomized crossover trial to determine if there is a significant difference in maximal and submaximal aerobic exercise capacity (VO₂ max; assessed during the CPET) in athletes with (arm 1) and without (arm 2) the use of a face covering.

Specific Aim 3: Describe participants' experiences' while wearing a face covering during exercise.

Specific Aim 4: Determine reliability of the Attitudes Toward Face Coverings Questionnaire

Primary Outcomes:

- VO₂ max during treadmill Cardiopulmonary Exercise Testing (CPET)
- Test duration (time) on a CPET

Secondary Outcomes

- Minute ventilation (VE) at max during CPET

- Subjective dyspnea rating (Borg) at max during CPET
- Subjective exertion rating (Borg) at max during CPET
- O₂ saturation at baseline, each stage, and recovery during CPET
- Blood pressure at baseline, each stage, and recovery during CPET
- Max heart rate during CPET
- Respiratory quotient at max during CPET
- Attitudes Toward Face Coverings Questionnaire
- Scale of Measuring Subjective Perceptions Questionnaire

Phase II:

Specific Aim 1: Describe the primary and secondary outcomes of participants during a Cardiopulmonary Exercise Test (CPET) on a cycle ergometer with (arm 1) and without (arm 2) the use of a face covering.

Specific Aim 2: Conduct a randomized crossover trial to determine if there is a significant differences in cognitive performance outcomes in participants with (arm 1) and without (arm 2) the use of a face covering. Cognitive performance will be measured by simple reaction time and accuracy on the SRT task.

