The CPET will be performed in an area with immediate access to an automated external defibrillator (AED). Resting blood pressure, heart rate, pulse oxygenation and will be measured and recorded. Explanation of the Borg dyspnea and exertion scales will occur by an Exercise Physiologist prior to beginning test. Each subject will be asked to perform the exercise test to the best of their abilities. At the beginning of the test, subjects will be instructed to perform a walking warm up of 3 minutes at 1.7 speed and 0% incline.

- The Borg Rating of Perceived Exertion (6-20) scale will be used during the test to assess subjective exertion
- The Modified Borg Dyspnea Scale (0-10) will be used to assess subjective shortness of breath.
- Intermittent blood pressure measurements and pulse oximeter measurements will be taken by an exercise physiologist and heart rate will be monitored constantly.

Testing will be terminated if any of the following occurs: (a) subject becomes symptomatic; (b) pain is reported; (c) subject wishes to terminate test; (d) unsafe drop in blood pressure or hypertension over 250/120 mmHg reported; or (e) subject reports a “20” on Borg RPE scale or “10” on Dyspnea scale. Other termination of the test is reserved for the clinical judgment of research staff to ensure safety of the subject. After termination

of the test, subject will be instructed to perform a walking cool-down of 3 to 5 minutes. After subject has completed cool-down, recovery blood pressure, heart rate and pulse oxygenation will be measured and recorded. After completion of the first test, subject will be scheduled for second CPET 7-10 days later to allow for adequate recovery. When data collection is complete, CPET data will be gathered from metabolic cart and matched with subject testing materials.

Phase II CPET Procedures:

Among individuals with history of COVID-19, an ECG will be performed prior to CPET procedures and will be monitored throughout the CPET.

The CPET will be performed in an area with immediate access to an automated external defibrillator (AED). Resting ECG (among individuals with history of COVID-19), blood pressure, heart rate, pulse oxygenation, and blood lactate will be measured and recorded. Explanation of the Borg dyspnea and exertion scales will occur by an Exercise Physiologist prior to beginning test. Each subject will be asked to perform the exercise test to the best of their abilities.

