A standard cycle ergometry ramp protocol⁷ will be designed for each participant as used in previous masking study.⁸ The initial workloads and incremental increases will be determined based on the subject's age and weight. The protocol consists of 1 minute of unloaded cycling, followed by a 2-minute warmup at 25 W. The exercise phase consists of continuous progressive increases in power output (25 W · min⁻¹) every three minutes until the subject is unable to maintain 50 rpm. This is followed by 4 min of active recovery at 20 W.

- The Borg Rating of Perceived Exertion (6-20) scale will be used during the test to assess subjective exertion
- The Modified Borg Dyspnea Scale (0-10) will be used to assess subjective shortness of breath.
- Intermittent blood pressure measurements and pulse oximeter measurements will be taken by an exercise physiologist and heart rate will be monitored constantly.
- Blood lactate will be measured pre and post-CPET using a Nova Medical Lactate Plus: Blood Lactate Measuring Meter-Version 2 device.

Testing will be terminated if any of the following occurs: (a) subject becomes symptomatic; (b) pain is reported; (c) subject wishes to terminate test; (d) unsafe drop in blood pressure or hypertension over 250/120 mmHg reported; or (e) subject reports a “20” on Borg RPE scale or “10” on Dyspnea scale. Other termination of the test is reserved for the clinical judgment of research staff to ensure safety of the subject. After termination of the test, subject will be instructed to perform a cycling cool-down of 3 to 5 minutes. After subject has completed cool-down, recovery blood pressure, heart rate and pulse oxygenation will be measured and recorded. After completion of the first test, subject will be scheduled for second CPET 7-10 days later to allow for adequate recovery. When data collection is complete, CPET data will be gathered from metabolic cart and matched with subject testing materials.

Disinfection Procedures

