Participant characteristics will be summarized with means and standard deviations or medians and interquartile ranges for numerical variables, and counts and percentages for categorical variables. The primary outcomes, VO₂ max and test duration, will first be assessed for normality using a Kolmogorov-Smirnov test prior to determining the analysis to be used. If the distribution meets the normality assumption, paired t-tests will be used to determine if there is a difference between participants when wearing and not wearing a face covering. If the distribution does not meet the normality assumption, Wilcoxon signed-rank tests will be used. All secondary outcomes will follow the same analysis plan of assessing the normal distribution assumption to determine the appropriate test for each outcome. Inter-rater reliability analysis will be conducted for the Attitudes for Face Coverings Questionnaire. All analysis will be performed using SAS 9.4 at a 0.05 significance level.

Risks & Benefits

- Physical risks: The potential risks include any and all risks associated with exercise including muscular injury, increased blood pressure and heart rate, and cardiac arrest. Other risks include hypoglycemia post-exercise and lightheadedness or syncope. Although some risks are unavoidable, the careful monitoring of signs and symptoms by the subject and clinical staff will minimize these risks.
- No psychological risks have been identified by participating in this study.
- No social risks have been identified by participating in this study.
- No economic risks have been identified by participating in this study.
- No legal risks have been identified by participating in this study.
- Potential benefits: Participants in this study may experience greater confidence in performing aerobic activities and may gain a better understanding of their personal functional exercise capacity at the time of testing. Participants may also better understand their body's response to exercise with and without a face covering which may impact training and performance in recreational and occupational ventures.

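### Recovery blood pressure and oxygen saturation are read after a cool-down of 3 to 5 min, so one person's masked and unmasked readings can fall 2 min apart in Phase I; Phase II is unclear

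*Combined protocol and SAP*

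**What the plan says.** Under Phase I CPET Procedures, a terminated test is followed by a "walking cool-down of 3 to 5 minutes. After subject has completed cool-down, recovery blood pressure, heart rate and pulse oxygenation will be measured". No minute after the end of exercise is set for the reading, no limit is put on the delay after cool-down, and the walking speed and incline are not given. The warm-up in the same section is fully specified: "walking warm up of 3 minutes at 1.7 speed and 0% incline".

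Phase II CPET Procedures carries two statements. The description of the ergometer protocol ends with "This is followed by 4 min of active recovery at 20 W". The paragraph on test termination then prescribes a "cycling cool-down of 3 to 5 minutes. After subject has completed cool-down, recovery blood pressure, heart rate and pulse oxygenation will be measured". The text does not say whether one replaces the other or whether they run in sequence.

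The readings are outcomes as well as safety checks. Specific Aims & Outcomes lists, as secondary outcomes in both phases, "Blood pressure at baseline, each stage, and recovery during CPET" and oxygen "saturation at baseline, each stage, and recovery during CPET". Under Data Analysis, if normality holds, "paired t-tests will be used to determine if there is a difference between participants when wearing and not wearing a face covering", with Wilcoxon signed-rank tests otherwise. It adds that "All secondary outcomes will follow the same analysis plan". Heart rate is read at the same moment, but the listed heart rate outcome is the maximum, so it is not affected.

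**The concern.** The crossover gains precision because each person is their own control. That works best when the two readings being subtracted are taken under the same conditions. Here the recovery reading is tied to the end of a cool-down whose length may differ between visits. Blood pressure is assumed to fall quickly in the first minutes after maximal exercise, so a reading at 3 min and one at 5 min would differ even if the mask did nothing. That difference enters the paired comparison as noise.

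What is at stake is precision at one time point of two secondary outcomes, which are also measured at baseline and at each stage. The comparison would be biased only if cool-downs were systematically longer in one condition. The plan does not prevent that, but nothing in it points that way. VO₂ max, test duration and the reaction-time task are obtained before recovery and are unaffected.

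**Working it through.** The plan gives no figure on this point, so there is none to reproduce.

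**Largest gap from the cool-down range alone**

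- Phase I: 5 − 3 = 2 min. An unlimited delay after cool-down could widen it.
- Phase II, if the 4 min at 20 W is the cool-down: 0 min.
- Phase II, if only the 3 to 5 min sentence applies: 2 min, as in Phase I.
- Phase II, if the two run in sequence: readings at 4 + 3 = 7 to 4 + 5 = 9 min, so again 2 min.

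**Illustrative size for systolic pressure**

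Every input in this list is an assumption; none comes from the documents.

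- Cool-down length is uniform on 3 to 5 min and unrelated to condition, with the reading at its end.
- Excess over rest at time t is E × 2^(−t/h), with E = 60 mmHg (range 40 to 80) and halving time h = 2 to 3 min.
- r is the correlation between a person's two visits: 0, 0.5 or 0.8.
- Within-pair SD from all other sources is 10 to 20 mmHg.

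Added within-pair SD = √(2(1 − r)) × SD of the excess over the uniform range.

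For E = 60, h = 2 and r = 0, the mean of 2^(−t/2) over 3 to 5 min is 0.2550 and the mean of its square is 0.0676. The SD is therefore 0.0508, and 60 × 0.0508 × √2 = 4.31 mmHg. The other cases follow in the same way:

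| r | Added SD at E = 60 (h = 2; h = 3) | Range, E = 40 to 80 | Pairs read more than 1 min apart |
|---|---|---|---|
| 0 | 4.31; 4.52 (about 4.4) | 2.9 to 6.0 | 25% |
| 0.5 | 3.05; 3.20 (about 3.1) | 2.0 to 4.3 | 9% |
| 0.8 | 1.93; 2.02 (about 2.0) | 1.3 to 2.7 | 1% |

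A simulation of 1,000,000 pairs with correlated uniform lengths agreed with these SDs within 0.02 mmHg and supplied the last column.

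A pair at the extremes, 3 v 5 min, differs by 60 × (2^(−3/h) − 2^(−5/h)) = 10.6 mmHg (h = 2) or 11.1 mmHg (h = 3). Over E = 40 to 80 the range is 7.1 to 14.8.

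**What that noise costs**

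The equivalent share of extra pairs is (added SD / other SD)²:

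- r = 0: (4.4/20)² = 0.048 to (4.4/10)² = 0.194, so 5% to 19%. Over the full range it is (2.9/20)² = 0.021 to (6.0/10)² = 0.36, so 2% to 36%.
- r = 0.5: (3.1/20)² = 0.024 to (3.1/10)² = 0.096, so 2% to 10%.
- r = 0.8: (2.0/20)² = 0.010 to (2.0/10)² = 0.040, so 1% to 4%.

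Standard error of the mean difference with 50 pairs (the planned maximum per phase) and r = 0:

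- Other SD 10: √(10² + 4.4²)/√50 = 1.55, against 10/√50 = 1.41 mmHg.
- Other SD 20: √(20² + 4.4²)/√50 = 2.90, against 20/√50 = 2.83 mmHg.

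**Phase II, sequential reading (7 to 9 min, r = 0)**

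Four minutes later, the excess is multiplied by 2^(−4/h). That gives 4.31 × 0.25 = 1.08 (h = 2) and 4.52 × 0.397 = 1.80 mmHg (h = 3), or 0.7 to 2.4 over E = 40 to 80. If the 4 min is the cool-down, the added SD is 0. If only the 3 to 5 min applies, the Phase I figures hold.

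No figure was computed for oxygen saturation.

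**The case against.** The strongest objection is that this matters little. Even with independent cool-down lengths, the least favourable correlation considered, the standard error moves only from 1.41 to 1.55 or from 2.83 to 2.90 mmHg. A single site, trained staff and the same person at both visits make some positive correlation plausible, and at 0.8 the gain is only 1% to 4% of pairs. No sample size and no inferential aim rests on the recovery reading. This stands, and it is why the point is a small improvement and not a flaw in the main comparison.

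The magnitude also rests entirely on assumed inputs. The model lets pressure decay towards its resting level while the participant is still walking. If it settles at a walking level instead, the part that decays is smaller and the figures overstate the noise. They scale in proportion to E, so the low end of the range is the better guide in that case. For oxygen saturation nothing has been quantified, and the argument there is only that its reading time varies in the same way.

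In Phase II, 4 min lies within 3 to 5 min, and the most natural reading is that the 4 min at 20 W is the cool-down. The spread is then zero and only the wording needs tidying. That is fair, but the text does not settle it, and staff could follow different sentences at different visits.

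Finally, a range gives staff latitude after a maximal test, and the reading is at least tied to the same event each time. But that event occurs at a variable time. Safety latitude survives a fixed reading time, because cool-down can continue after the reading. The case report forms are not in the documents, so the time may already be recorded; the protocol does not require it.

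**Conclusion.** The concern holds as a minor, inexpensive improvement. In Phase I the stated rule permits a 2 min gap between a person's two recovery readings from the cool-down range alone, and more if the reading is delayed. In Phase II the gap is 0 or 2 min depending on which sentence governs.

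The 2 min follows from the text; its effect in mmHg is illustrative. It depends on the assumed excess, halving time, spread of cool-down lengths, correlation between visits and background SD. The damage is lost precision at the recovery time point only. Confidence in the practical importance is medium.

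**What to change.** Set the cool-down to 4 min at both visits in both phases.

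- **Phase I:** 4 min of walking at one stated speed and incline; the warm-up settings would serve.
- **Phase II:** replace the two recovery sentences with one, giving 4 min at 20 W whatever the reason for stopping, unless safety requires otherwise.
- **Both phases:** take the recovery readings immediately at the end of the 4 min, in the same posture and activity state at both visits, and record the actual time since test termination.

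The cost is protocol wording and one time field on the case report form. Staff lose a little flexibility over cool-down length. A longer cool-down needed for safety can continue after the reading, and if the reading itself must wait, its recorded time shows by how much. The spread due to cool-down length then falls to zero apart from such exceptions.

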Specific Aim 3: Describe differences in outcomes between participants with and without previous history of COVID-19 diagnosis

Primary Outcomes:

- VO₂ max during CPET
- Test duration (time) on a CPET
- Reaction time (measured in milliseconds) and percentage accuracy on the SRT task

Secondary Outcomes:

- Minute ventilation (VE) at max during CPET
- Subjective dyspnea rating (Borg) during CPET
- Subjective exertion rating (Borg) during CPET
- O₂ saturation at baseline, each stage, and recovery during CPET
- Blood pressure at baseline, each stage, and recovery during CPET
- Max heart rate during CPET
- Respiratory quotient at max during CPET
- Blood lactate during CPET

[figure not shown]
INVESTIGATIONAL PLAN

Research Design and Methodology

Phase I:

In this prospective, randomized crossover trial of eligible athletes, we will compare VO₂ max during two maximal cardiopulmonary stress exercise tests (CPET), seven to ten days apart. Subjects will be randomized into either the face covering or non-face covering group using a 1:1 randomization scheme, stratified by sex, and will serve as their own control in the subsequent test seven to ten days later (see Figure 1. Randomization diagram, below). A within-subjects analysis will be performed stratified by sex.

[figure not shown]
Figure 1. Phase I Randomization diagram

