Presence of beards	Beards interfere with the fit of the Vo2 mask. Therefore, participants with beards will be asked to shave prior to their visit. If they are unwilling to shave, they will not be eligible for the study.
Claustrophobia	Participants who have been diagnosed or treated for claustrophobia will be excluded. Claustrophobia is a contraindication of the CPET test.
Currently experiencing symptoms of COVID-19 or < 7 days since last symptoms	Participants will be screened for COVID-19 symptoms using the BSW COVID-19 screener; if participants have past history of COVID-19 based on laboratory testing, participants will be ineligible if <7 number of days since last symptoms

Study Procedures

Phase I & II Subject Recruitment

Up to 100 participants (50 for each phase) will be recruited from Baylor Scott & White Sports Therapy and Research at The Star in Frisco, Texas through approved fliers, calls, emails, and social media, as well as through local community organizations, healthcare clinics, and collaborating centers and organizations, including but not limited to the Sports Academy and the University of North Texas. IRB-approved fliers will be posted at BSW The Star and at affiliated organizations and collaborators in the DFW Metroplex and surrounding areas. In addition, members of the study team will attend meetings with local clinicians and community partners to inform them of the purpose of the study. The study flier will contain information on the study and methods to contact the study team including (1) a QR code linked to the eligibility screener which will be stored in a REDcap, a HIPAA-compliant (21 CFR Part 11) secure web application, (2) a phone number, and (3) an email address of the study coordinator. Interested individuals may contact the study team by phone or email to learn more about the study and undergo a telephone screener or follow the QR code to complete the eligibility screener electronically. A snowball sampling technique will be used for further recruitment whereby interested participants will be invited to ask other athletes they know to contact the study team about participation. Eligible individuals will be contacted by a member of the study team to schedule their first study visit. It is anticipated that recruitment will take 2-4 weeks during each phase to achieve our desired sample size.

Subject Information and Screening

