Phase I & II: Participants meeting the inclusion and exclusion criteria will be approached, screened, consented, and enrolled into the study. After obtaining informed consent, participants will be randomized to either complete their first test with no face covering or with a face covering in a 1:1 randomization ratio stratified by sex. A random number generator will be used to pre-determine the randomization group for each participant ID number. The group assignment will be not be revealed to either the participant or the study staff until informed consent is complete.

Cardiopulmonary Exercise Testing (CPET)

During the screening process, subjects will be encouraged to abstain from nicotine and caffeine prior to the test. Subjects will be scheduled to perform a CPET on a treadmill with (arm 1) and without (arm 2) a face covering (with testing for each arm seven to ten days apart). A face covering will be provided to participants randomized into the face covering group, with the option for participants to keep their face covering at the end of the assessment. Subjects will be fitted for metabolic testing (K5 CPET, COSMED, Concord, CA) equipment according to factory requirements. <https://www.cosmed.com/en/products/cardio-pulmonary-exercise-test/k5>

The use of new cloth face coverings beneath the K5 mask will be standardized, with face coverings consisting of the same material and cut/design for each participant (which the participant then keeps or discards). The correct fitting and leak tightness will be confirmed before each test for each subject. This will be achieved through (a) inspiration and (b) expiration with maximal force. During both maneuvers, the valve of the mask is closed leading to abrupt stop of the air flow. The fitting is carefully checked for the absence of any acoustic, sensory or visual indication of leakage (e.g., lifting of the mask, whistling or lateral airflow) by the investigators and the test person.

Phase I CPET Procedures:

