Initial visit/Visit 1	
 • COVID-19 screening and temperature check is performed • Demographic information (age, race, ethnicity, sex, income, insurance, work history, sport) • Clinical and physical activity information (Physical activity readiness questionnaire, physical activity history, tobacco use, marijuana use, vaping, history of asthma, height, weight, use of beta-blockers) • Attitudes Towards Face Coverings Questionnaire • Cardiopulmonary exercise testing (CPET) 
 ◦ Dyspnea scores ◦ Exertion scores ◦ Pulse ox measurements ◦ Blood pressure measurements • Scale of Measuring Subjective Perceptions • Participant will be scheduled for 2nd CPET
Visit 2	
 • COVID-19 screening and temperature check is performed • Attitudes Towards Face Coverings Questionnaire • Cardiopulmonary exercise testing (CPET) 
 ◦ Dyspnea scores ◦ Exertion scores ◦ Pulse ox measurements ◦ Blood pressure measurements • If subject is randomized to face covering: Qualitative question describing experience • Quantitative and qualitative questions about difficulty of wearing face coverings during CPET and differences completing the CPET with and without a face covering. • Scale of Measuring Subjective Perceptions

Phase II:

Study Visit	Visit Details
Initial visit/Visit 1	
 COVID-19 screening and temperature check is performed Demographic information (age, race, ethnicity, sex, income, insurance, work history, sport) If subject reports a previous COVID-19 diagnosis: information regarding symptoms, severity, hospitalization, health changes, experience while exercising, and vaccinations will be collected. Clinical and physical activity information (Physical activity readiness questionnaire, physical activity history, tobacco use, marijuana use, vaping, history of asthma, height, weight, use of beta-blockers) Attitudes Towards Face Coverings Questionnaire ECG among individuals with history of COVID-19 Cardiopulmonary exercise testing (CPET) 
 Heart rate Dyspnea scores Exertion scores Pulse oximetry measurements Blood pressure measurements Lactate measurements (pre and post-CPET) Scale of Measuring Subjective Perceptions Participant will be scheduled for 2nd CPET

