Visit 2	
 COVID-19 screening and temperature check is performed Attitudes Towards Face Coverings Questionnaire ECG among individuals with history of COVID-19 Cardiopulmonary exercise testing (CPET) 
 Heart rate Dyspnea scores Exertion scores Pulse oximetry measurements Blood pressure measurements Lactate measurements (pre and post-CPET) When subject is randomized to face covering: Qualitative question describing experience Quantitative and qualitative questions about difficulty of wearing face coverings during CPET and differences completing the CPET with and without a face covering. Scale of Measuring Subjective Perceptions

Compensation and Costs

While we will not pay participants for taking part, participants will be reimbursed a \$50 Visa gift card for their time/effort to attend each of the assessments (two) which are required for research for a total of \$100. Participants will be given the option to keep their face covering that was given to them during CPET testing. Participants will not incur any additional research-related costs due to study participation.

Data Protection & Confidentiality

In order to assure participant confidentiality, all participants will be assigned a unique study identification number. Only one master list will be maintained by the PI and the study coordinator on a secure network drive in a password protected file. All case report forms and databases will use the subject ID number rather than names or other private health information and entered into REDCap. All paper documentation, including

signed paper consent forms and case report forms will be maintained by the PI behind a locked door in a locked file cabinet.

All participants that are screened will be given a screening identification number. Screening reports will not use private health information and will only refer to patients using the screening identification number. After consent, participants will be given a unique subject ID. All documents thereafter will refer to the participant by subject ID. All screening and enrollment data will be tracked on a password protected enrollment tracking spreadsheet which will also contain the link to identifiers. Only authorized study personnel will have access to this database. All data will be shared on the secured Baylor Network Onedrive server.

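### The open question on mask experience is listed only at Visit 2, so at least about half of participants are not asked it at their masked test

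*Combined protocol and SAP*

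**What the plan says.** Phase I Specific Aim 3 is to "Describe participants' experiences' while wearing a face covering during exercise". It is not restricted to one order of testing.

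The Randomization section, which covers both phases, says that "participants will be randomized to either complete their first test with no face covering or with a face covering in a 1:1 randomization ratio". The Phase I design paragraph adds that subjects "will serve as their own control in the subsequent test seven to ten days later". Everyone who completes the study therefore has one masked and one unmasked test.

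In the Schedule of Assessments, the Visit 1 row of each phase has no open question on mask experience. The Visit 2 row has "Qualitative question describing experience", under the condition "If subject is randomized to face covering" in Phase I and "When subject is randomized to face covering" in Phase II. The next Visit 2 entry carries no condition: all participants get quantitative and qualitative questions on how hard the covering was to wear and on how the two tests differed. Dyspnea and exertion scores and the Scale of Measuring Subjective Perceptions are listed at both visits.

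**The concern.** An item about what it was like to exercise in a mask is best asked straight after the masked test. Under randomized order that test falls at either visit, but the item is fixed to Visit 2.

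The condition attached to it is also unclear. In a crossover every participant wears the covering, so being randomized to it does not tell staff whom to ask. It may mean that today's test is masked. It may instead mean the group assigned to mask first, which fits the Research Design section, where subjects are randomized into a face covering or a non-face covering group.

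At stake is the completeness of the open-ended material for Phase I Aim 3, and whether it represents both test orders. Same-day impressions not collected at Visit 1 cannot be recovered later.

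**Working it through.** The documents give no figure for how many participants answer this item, so there is nothing to reproduce. The check sets the schedule against the randomization.

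**Inputs**
- Participants per phase: 50, a ceiling. Subject Recruitment: "Up to 100 participants (50 for each phase) will be recruited".
- Allocation: 1:1 on test order (Randomization).
- Interval between tests: 7-10 days (CPET procedures, both phases).
- Placement of the item: Visit 2 only, conditional (Schedule of Assessments, both phases).

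**Masked tests at Visit 1.** Expected number = 50 × 1/2 = 25 per phase, which is 25/50 = 50%. The documents do not mention blocking. If randomization is simple and unblocked (an assumption), the number is Binomial(50, 0.5), and the range 18 to 32 has exact coverage of 96.7%.

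**Who is asked, under each reading of the condition (full enrolment, no dropout)**

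| Reading | Mask-first (about 25) | Mask-second (about 25) | Asked at the masked test |
|---|---|---|---|
| A: masked at this visit | Never asked | Asked at Visit 2, after the masked test | About 25 of 50 |
| B: assigned to mask first | Asked at Visit 2, after the unmasked test and 7-10 days after the masked one | Never asked | 0 of 50 |

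On reading A, about 50 − 25 = 25 are missed at the masked test. On reading B, all 50 are missed. The loss is therefore at least about half, and the figure of 25 belongs to reading A only.

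**After the fix.** If the item follows the masked CPET at whichever visit that occurs, 50 of 50 are asked at the masked test, before dropout.

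**Withdrawal.** The Study Withdrawal section lets subjects leave at any time. A mask-first participant who leaves after Visit 1 has worn the mask but reaches neither the open item nor the difficulty questions, since both are at Visit 2. The documents give no dropout rate, so this loss cannot be sized.

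**The case against.** The strongest case against the point is that little depends on this item, and that the schedule collects other experience data from everyone. Borg dyspnea and exertion ratings are taken at both visits, hence at every masked test. The Scale of Measuring Subjective Perceptions is also given at both visits and is a Phase I secondary outcome. The unconditional Visit 2 questions ask all participants, partly in open form, about difficulty and differences. The open item itself is not a listed outcome and has no stated analysis.

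Most of this stands, and it limits the consequence. It does not close the gap. The difficulty questions rely on 7-10 day recall, after an unmasked test, for mask-first participants, but are same-day for the mask-second group. The content of the perceptions scale is not given, so it cannot be assumed to replace an open question. The plan also lists the open question as a separate item.

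The Phase II wording (When rather than If) may suggest that the item was meant to follow the masked test. That is inference: the item is still absent from the Visit 1 row.

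Three stronger readings are tempting, and the documents do not support them:
- *Half of the Aim 3 data are lost.* The shortfall concerns one open-ended item, and mask-first participants still report on the mask through the measures above.
- *Mask experience is confounded with order.* Aim 3 is descriptive, and the Data Analysis section plans no contrast on this item. Under reading A the respondents are a randomly allocated half, all answering after a masked test. What is limited is their number and how far they represent participants masked in the first period.
- *Aim 3 is harmed in both phases.* Phase II Aim 3 concerns COVID-19 history, and no Phase II aim depends on this item.

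Recall in the with/without comparison is not a fault in itself. That comparison can be asked only after both tests.

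**Conclusion.** The point holds as a scheduling defect of modest consequence that is worth correcting. As written, about 25 of 50 participants per phase are never asked the open question (reading A), or nobody is asked it at the masked test (reading B). These counts assume full enrolment of 50, 1:1 allocation of order and no dropout.

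The effect is on the completeness and representativeness of one descriptive item for Phase I Aim 3. In Phase II the same gap is an inconsistency in the schedule and harms no stated aim. VO₂ max, test duration and the reaction-time outcomes are unaffected.

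**What to change.** In both schedules, list the open experience question at Visit 1 and at Visit 2, on the condition that this visit's CPET was performed with a face covering, and have it asked right after that test. This also replaces the ambiguous condition. Keep the with/without comparison questions at Visit 2 for everyone.

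The cost is one edit to the schedule and one to the case report form in each phase. No visit is added, and each participant is asked the item once.
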